4.2 Consenting processes

WP5

5.1 Prototype testing by clinical engineering

5.2 Virtual training session on data collection processes for participants (1 hour)

5.3 Baseline data collection period (2 weeks)

5.4 In person training session on prototypes (1- 1.5 hours)

5.5 Intervention period using prototypes (3 months)

5.6 'JIA Toolbox' returned to SCH

5.7 post-intervention data collection period (2 weeks)

5.8 End of intervention interview (1 hour 1:1 with researcher)

WP6

6.1 Analyse qualitative data with healthcare professionals who are a part of the research team

The end of study is defined as the date of the last interview of the last participant.

As 'JIA Toolbox' consists of therapeutic self-management tools, participants will decide when to use the prototypes during the 3-month intervention period. As such, there should be no added burden to the participants in using these products, as they are designed to assist with condition management rather than hinder. There will be two training sessions, one on how to use the data collection packs (examples shown in appendix 3) and one on how to use the prototypes. This will ensure that the participants are clear on what they should do, minimising any potential risks in interacting with the prototypes. There will be regular weekly check ins to ensure participants are happy with the study and to troubleshoot any issues raised. The 3-month intervention period where the participants are using the devices will take place over August, September and October, giving CYP 1 month to get used to the devices prior to using them in a school context. From the previous proof-of-concept study, it was highlighted that the devices were beneficial in building CYP-teacher relationship near the beginning of the school year. Post-intervention interviews will be conducted at the end of the study to ensure all experiences are equally captured and to give participants the opportunity to highlight anything they feel needs additional clarification.

The study design has had input from YOUR RHEUM which is a group of CYP (11-24) with diagnosed rheumatic conditions, and JAR which is a group of CYP (7-25) with Juvenile Arthritis. Both groups regularly input on CYP rheumatology research. They have a strong track-record in advising on and shaping rheumatology research and represent a 'Gold Standard' approach to PPI involvement. These groups have been involved in shaping the study design and participant facing materials such as the data collection packs to ensure they are appropriate and will be effective. They have also commented on the prototypes themselves, feeling that they fulfill key unmet needs within the JIA population. [name] and [name] are both healthcare professionals who work within

rheumatology and come into regular contact with CYP with JIA. They are both members of the project team and have been involved in planning the study design, utilising their extensive knowledge of the condition to ensure it is appropriate and capturing useful data. This project is being funded by Medical Research Council and as such, had to go through a rigorous application process.

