5.0 Study Design

CYP aged 7-16 years with JIA, parents/guardians and HCPs based at Sheffield Children's Hospital (SCH) and/or a part of Juvenile Arthritis Research (JAR) charity will participate throughout this study.

The components of 'JIA Toolbox' are illustrated in Appendix 1. The potential impact of these devices will be assessed by comparing baseline qualitative data about living with JIA, with data collected when the devices are in use. Post-intervention interviews with participants will capture practical usability issues and the potential impact of 'JIA Toolbox' on CYP's wider life, like social impact, to frame possible outcome measures for future evaluation.

The study design is shown in Appendix 2. It will consist of:

WP4

4.1 Recruitment of participants n=25 (CYP aged 7-16) and their parents/guardian from SCH or JAR

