11.0 Ethical Considerations

1. Risk of unintended distress

Discussion with participants about JIA will be treated sensitively. Interviews may lead to minor distress. To minimise this risk, participants will be informed they do not have to complete any questions or take part in any activities that make them uncomfortable and reminded that they have the right to withdraw at any point and will still receive their thank you voucher. If a participant becomes distressed, the session will be ended sensitively but quickly. Any participant who has shown evidence of distress will be discussed with the study clinicians (DH/CD). The rheumatology team has a clinical psychologist who could be involved if significant distress is felt to have occurred, although it is not anticipated this will be needed.

2. Burden of time

Involvement is optional and participants will receive a 'thank you' voucher. The use of the prototypes is designed to fit around day-to-day activities and to assist rather than be a burden. Difficulty in using the products will be minimised through training and weekly check ins where the project team can trouble shoot any queries.

3. Concern that they can't withdraw

Before each part of the study, participants, parents and guardians will be informed that this is a voluntary research study and they are free to withdraw at any point and it will not affect their future healthcare.

4. Risk of unintentionally worsening symptoms

The prototypes are designed to help improve symptoms and are based upon proven therapies and known and tested technologies that are routinely used in other products on the market, therefore this risk is minimal. Based on the proof-of-concept study, the prototypes were seen as beneficial to symptom manage and did not make any participants symptoms worse.

5. Using the prototypes

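### The only outcome interview comes at the end of the study and no exit contact is described, so equal capture of experiences is not supported for children who withdraw

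*Protocol*

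**What the plan says.** The schedule in section 5.0 of the protocol runs: two weeks of baseline collection (5.3), three months of device use (5.5), return of the Toolbox (5.6), two weeks of post-intervention collection (5.7), then a single one-to-one interview (5.8). The interview's purpose is stated in the same section: "Post-intervention interviews with participants will capture practical usability issues and the potential impact of 'JIA Toolbox' on CYP's wider life". The reason given for its timing is "Post-intervention interviews will be conducted at the end of the study to ensure all experiences are equally captured".

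Section 11.0 plainly foresees withdrawal. Families are to be told that "they have the right to withdraw at any point and will still receive their thank you voucher", and again that "they are free to withdraw at any point and it will not affect their future healthcare". The same section lists "4. Risk of unintentionally worsening symptoms" and the use of electronic prototypes among the risks.

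Three other statements bear on the point. Section 5.0 provides weekly check-ins for troubleshooting, bases the assessment of impact on baseline data compared with data gathered during device use, and leaves it to participants when to use the devices. Section 9.0 gives a green light if 50% report a positive change, amber at 30% and red at 10%, with no denominator. Section 15.0 presents early discovery of barriers to adoption as a benefit of the design.

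**The concern.** The protocol claims a property for its interview timing that the schedule delivers only for children who stay to the end. A family that withdraws during the three months reaches neither step 5.7 nor step 5.8, and no visible step replaces them.

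The loss is unlikely to be random. Lack of benefit, a device that is awkward to use, or symptoms that feel worse are all plausible reasons to leave, and the interview exists to record such experiences. A study meant to find barriers to adoption would hear least from the children who met a decisive one. Section 6.0 treats a teacher's refusal to take part as informative about adoption; a child's departure is informative for the same reason.

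The progression decision is also exposed. If the percentage in section 9.0 is taken over interviewed children only, each non-improver who leaves drops out of the denominator and the percentage rises. An analysis plan could fix the denominator, but it could not recover interviews that were never offered.

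**Working it through.** **Step 1: the text side by side.**

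| Question | Protocol | Consequence for a child who withdraws |
|---|---|---|
| When is the interview? | Once, after 5.5, 5.6 and 5.7 | Not reached |
| Can families leave earlier? | Yes, at any point, keeping the voucher (11.0) | Foreseen, with no data step attached |
| Is there contact before leaving? | Weekly check-ins (5.0, 11.0) | Trouble may surface, but recording as study data is not stated |
| Are there other data? | Baseline and in-use data (5.0) | Partial data may exist up to the time of leaving |
| What if a child only stops using a device? | Use is at the child's discretion (5.0) | Not a withdrawal; interview still due |

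**Step 2: inputs for the effect on the decision.** From the protocol: N = 25 and a green threshold of 50% (section 9.0). Section 9.0 supports 25 by citation, with no precision or dropout input, so there is no calculation to reproduce. Not in the protocol: the dropout rate, and whether the STOP/GO report comes from the interview. Assumptions: d withdrawals, d = 0 to 8; every leaver is a non-improver; 50% is read as at least 50%. The budget in section 12.0 covers 30 vouchers against 25 participants without explanation. If the 5 extra were a dropout allowance, that would be 5/30 = 16.7%, but the protocol does not say so.

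**Step 3: simple illustration.** Take d = 5 and 10 positive reports, all among the 20 completers.
- Completers only: 10/20 = 50%, green.
- All enrolled: 10/25 = 40%, below green.

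**Step 4: positive reports needed for green.** With all 25 as denominator, 0.5 × 25 = 12.5, so 13 are needed. With completers only, the number is 0.5 × (25 − d), rounded up.

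| d | Completers | Needed for green | As a share of 25 |
|---|---|---|---|
| 0 | 25 | 13 | 52% |
| 3 | 22 | 11 | 44% |
| 5 | 20 | 10 | 40% |
| 8 | 17 | 9 | 36% |

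**Step 5: chance of a green light.** Let p be the true positive share of all 25. Since leavers are all non-improvers, the completers' rate is q = 25p/(25 − d), and the number positive is taken as binomial(25 − d, q). For p = 0.40 and d = 5, q = 10/20 = 0.50, and the chance of at least 10 of 20 is 0.59.

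| d | p = 0.40, completers only | p = 0.40, all 25 | p = 0.30, completers only | p = 0.30, all 25 |
|---|---|---|---|---|
| 0 | 0.15 | 0.15 | 0.02 | 0.02 |
| 3 | 0.41 | 0.14 | 0.09 | 0.01 |
| 5 | 0.59 | 0.13 | 0.18 | 0.01 |
| 8 | 0.77 | 0.11 | 0.31 | 0.01 |

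Part of the rise from d = 0 to d = 3 is rounding: 13 of 25 is 52%, while 11 of 22 is exactly 50%. The main cause is the shrinking denominator.

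**The case against.** The strongest reply is that the interview is not the only source. Weekly check-ins would give a child who has trouble in week 3 about two earlier occasions to say so. Distressed participants are discussed with the study clinicians. Baseline and in-use data may already be in hand when a child leaves. A child who dislikes a device can put it aside and remain in the study. The timing sentence can also be read as interviewing everyone at a common point, which is accurate for those who stay. Information sheets, consent forms, data packs and the risk assessment form are cited but not shown, and may say what is asked of a withdrawing family. Finally, section 11.0 reports that no participant's symptoms worsened in the proof-of-concept study.

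Much of this stands, and it rules out two stronger readings. A reader might infer that children who leave because of worsening or device trouble are never asked about it. The documents do not support that, because check-ins and in-use data come before any departure. A reader might also infer that the equal-capture statement is simply false. The common-timing reading and the unseen appendices allow no more than that it is unsupported for children who withdraw.

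What does not stand is that these provisions close the gap. Check-ins are described as support and troubleshooting, are not said to be recorded for analysis, and are not said to continue after withdrawal. The proof-of-concept study is reassuring, but its cohort was 10 children (section 3.0).

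**Conclusion.** The point holds in limited form. For children who withdraw from the study, the protocol describes no exit contact and no recording of reasons, so its statement that end-of-study interviews capture all experiences equally is not supported. It can be supported for children who stay, including those who stop using a device.

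The direction of any bias is probably in favour of the Toolbox, but its size is unknown. The shift from 40% to 50%, and the rise in the chance of a green light from 0.15 to 0.59 at a true share of 40%, both rest on 5 assumed withdrawals, all non-improvers, and on a denominator of interviewed completers. They show how sensitive the rule is and predict nothing. With no withdrawals the problem disappears; with all 25 as denominator the chance of green stays at 0.11 to 0.15. No figure for unreported worsening can be derived from the document. The change is cheap and worth making before recruitment.

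**What to change.** In section 5.0, extend step 5.8 so that families who withdraw early are offered the interview, or a short optional phone version, at the time of withdrawal. It should cover the reason for leaving, any worsening and any device problem. State that the content of weekly check-ins is kept as study data. Report early leavers beside completers, with reasons where given. In section 9.0, give the STOP/GO percentage with all enrolled children as denominator. Limit the equal-capture wording to those who complete, or delete it.

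The cost is a few sentences in the protocol, a line in the information sheets and consent forms, and the effort of logging check-ins. The exit interview brings forward one already planned. Some families will decline, which must be respected, and leavers' interviews will fall at a different time from completers', so the two groups should be described separately.

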6.0 Participant Recruitment

The study will recruit from SCH Rheumatology service. [name] (DH) or CD will initially approach potential participants using a recruitment flyer (shown in appendix 2) for context (also available through SCH Rheumatology Facebook group). Interested participants will be screened by clinical members of the study team and given a participant information sheet (shown in appendix 5,6,7,8). Following this, they will give verbal consent for [name] (Principal Investigator) to call them for any queries. A consent form (shown in appendix 9, 10 and 11) will then be emailed to be signed and sent back.

The study will also recruit from JAR charity. They have a group of members who have agreed to be contacted about research opportunities. The process would involve me sending the recruitment poster to JAR which they would circulate among their members. JAR would then send an email with a form to fill in to register interest. This form would ask for details around the child's age (to check eligibility) and other inclusion criteria as well as their contact details which by submitting the form they would agree to be shared with UA. That list would then be sent to UA, who would then call each interested participant and if they would like to take part UA would then send through the Participant information sheets. After reading the PIS, if they would like to join the study UA will then send them the consent form for them to sign and return. UA has spoken with the director of JAR, [name] who is happy with this approach.

The process for recruiting and consenting teachers hinges upon which CYP have consented to be involved, as it is their teacher(s) that will need to be recruited. Once interested CYP and their parent/guardian have been consented. UA or CD will approach the CYP's school/teacher with a recruitment flyer for context. If interested, they will be given a participant information sheet. If they wish to proceed, a call will be arranged with the study lead UA for any queries. A consent form will then be emailed to be signed and sent back. If their teachers do not want to participate, this will still be useful data as it speaks to adoption of the intended prototypes. However, it is expected that at least 50% of CYP's teachers will engage with the study as the prototypes are designed to assist them in their role, in terms of helping and communicating with CYP. Based on the proof-of-concept study 100% of CYP's teacher's engaged, and we therefore expect similar engagement.

Families who participate in the study will receive a £50 'thank you' voucher recognising their time and involvement. The participation gift will be mentioned in the participant information sheet, once the participants have expressed an initial interest in WP4, after seeing the flyer. Teachers will not receive financial remuneration due to the fact that the prototype

pertaining to them is designed to assist duties that fall within the remit of their role in terms of helping and communicating with CYP.

Recruitment flyers, participant information sheets, consent and assent forms are shown in Appendix (5,6,7,8,9,10 and 11).

6.1 Selection of Participants

Inclusion Criteria

- Aged 7- 16 years (minimum age is 7 to ensure participants can adequately engage with the prototypes and describe their experience)
- Diagnosis of JIA
- Currently experiencing JIA symptoms
- Currently managed within SCH Rheumatology Service
- Fluent in verbal and written English
- Access to a computer with an internet connection to facilitate virtual co-design workshops due to the COVID-19 pandemic

Exclusion Criteria

- Aged <7 years or >16 years
- Non-fluent in verbal and written English
- Diagnosis of autistic spectrum disorder (ASD)
- Children with medically unexplained pain, pain amplification syndromes or other pain disorder
- Co-existing joint or muscle disorder other than JIA

We have excluded CYP with ASD because it can affect sensory processing including the interpretation of pain and may also affect how CYP are able to communicate. We have excluded CYP with other pain disorders because this would likely behave and respond differently to pain associated with JIA. We have excluded CYP with any co-existing joint or muscle disorder other than JIA because these may behave or respond differently to symptoms associated with JIA.

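### Section 6.1 requires care at SCH, but Sections 5.0 and 6.0 recruit through the JAR charity without that limit, and no clinical screening is described for the JAR route

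*Protocol*

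**What the plan says.** Protocol Section 6.1 gives six inclusion criteria. One is "Currently managed within SCH Rheumatology Service". It carries no alternative for children reached in another way.

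Protocol Section 5.0 describes the participants as "based at Sheffield Children's Hospital (SCH) and/or a part of Juvenile Arthritis Research (JAR) charity", and its work-package list plans "Recruitment of participants n=25 (CYP aged 7-16) and their parents/guardian from SCH or JAR".

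Protocol Section 6.0 first describes the hospital route, on which "Interested participants will be screened by clinical members of the study team". It then states: "The study will also recruit from JAR charity". On that second route the charity circulates the poster to its members and sends them a registration form. Of the form it says: "This form would ask for details around the child's age (to check eligibility) and other inclusion criteria as well as their contact details". The list goes to the lead researcher, "who would then call each interested participant and if they would like to take part UA would then send through the Participant information sheets". The consent form follows once the family has read the information sheets and wishes to join.

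Section 6.1 also gives five exclusion criteria. For three of them (autistic spectrum disorder, other pain disorders, other joint or muscle disorders) it adds a scientific reason: pain, symptoms or communication may differ in these children.

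**The concern.** Staff cannot follow both rules. If Section 6.1 governs, a JAR member under another hospital cannot be enrolled, and the JAR route yields only children whom the SCH service already manages and could approach directly. If Section 5.0 governs, such a child is enrolled in breach of a written inclusion criterion.

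The second issue is who establishes eligibility. The protocol assigns this to clinicians on one route and to nobody in particular on the other. The exclusions with no described check on the JAR route are the ones that the protocol itself justifies as bearing on how a child experiences or reports symptoms. Section 9.0 decides whether to go on to a larger study from the percentage reporting a positive change in condition management. A child who should have been excluded would count in that percentage like any other.

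**Working it through.** The protocol gives no figure to reproduce on this point. The check is a comparison of sections, with some counting.

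**1. Place of care**

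| Source | Rule | JAR child treated outside SCH |
|---|---|---|
| Section 6.1, inclusion criteria | must be under the SCH rheumatology service | not eligible |
| Section 5.0, opening sentence | SCH and/or JAR | within the study population |
| Section 5.0, step 4.1 | SCH or JAR, n=25 | may be recruited |
| Section 6.0, JAR route | poster and form go to JAR members, no SCH limit stated | invited |

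No other section reconciles these.

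**2. How many places are affected.** The protocol states no split between the routes. If Section 6.1 is applied literally, children outside SCH can fill 0 of the 25 places. If Section 5.0 is followed, they could fill any number from 0 to 25, each failing the written criterion. Nothing in the document narrows that range.

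**3. Screening steps as described in Section 6.0**

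| Step | SCH route | JAR route |
|---|---|---|
| First approach | clinical co-investigators, with flyer | charity circulates poster |
| Eligibility | screened by clinical team members | family-completed form: age, other inclusion criteria |
| Next contact | information sheet, then call | call from the lead researcher, then information sheets |
| Consent | form emailed, signed and returned | form sent, signed and returned |

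The section on the research team gives the chief investigator's expertise as design, not clinical care. No eligibility check is assigned to the lead researcher's call.

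**4. What a form limited to inclusion criteria would catch**

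| Exclusion criterion | Mirrored by an inclusion criterion? |
|---|---|
| Age below 7 or above 16 | yes |
| Not fluent in English | yes |
| Autistic spectrum disorder | no |
| Medically unexplained pain, pain amplification or other pain disorder | no |
| Other joint or muscle disorder | no |

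So 2 of the 5 exclusions would be caught, and 5 − 2 = 3 would not. The JIA diagnosis is an inclusion item, so the form would ask for it, but on this route it would rest on the family's report.

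**5. Weight of one child in the STOP/GO rule.** Assume that the denominator is the 25 children, which Section 9.0 does not say outright. Each child then counts 1/25 = 4 percentage points against the cut-offs of 50%, 30% and 10%.

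**The case against.** The strongest defence is that JAR is only another way of reaching SCH patients. The form asks about the other inclusion criteria, and read literally these include care at SCH. Children treated elsewhere would then be turned away at registration and never enrolled. Every remaining JAR recruit would be known to the service in which the clinical co-investigators work, so an unconfirmed diagnosis would be a much smaller worry. It could be added that the opening sentence of Section 5.0 is loosely built and may attach its hospital-or-charity phrase to the health professionals.

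Part of this stands. It shows that the screening gap matters most if the SCH criterion is not enforced. It does not remove the contradiction: step 4.1 applies the SCH-or-JAR choice to the children themselves, and Section 6.0 does not restrict the mailing to SCH patients. A form that enforced Section 6.1 would reject children whom Section 5.0 admits. Even under this defence, no clinical check is assigned on the JAR route.

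Two stronger readings are tempting, and the document does not support them.

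- A reader might infer that the JAR form leaves out the exclusion criteria and that excluded children enter unchecked. The form is not shown, Section 6.0 only summarises it, and the content of the researcher's call is not specified. What can be said is that no check is described, and that this concerns three exclusions, not all five.
- A reader might put a number on the loss of precision by supposing that some of the 25 are later dropped as ineligible. The protocol gives no split and no rule for dropping enrolled children, and its STOP/GO rule uses no confidence interval. Such a figure would rest on invented inputs.

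**Conclusion.** The contradiction over place of care is explicit and unresolved, and it must be settled before recruitment through JAR. Its reach is 0 to 25 of the 25 places, because the split is not stated. A breach arises only when a child from outside SCH is actually enrolled.

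The screening point holds in a narrower form. The protocol describes clinical screening for the SCH route only. For the JAR route it describes no check of three clinical exclusions and no confirmation of diagnosis. This rests on the summary of the form in Section 6.0, and the form itself may ask more. If the procedure is followed as written, children whom the protocol means to exclude could be enrolled and counted in the STOP/GO percentage. How many cannot be estimated from the document.

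**What to change.** Reconcile Sections 5.0, 6.0 and 6.1 in one of two ways; the choice of population is the sponsor's:

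- widen the place-of-care criterion in Section 6.1 so that it covers the children whom the JAR route is meant to reach; or
- keep the criterion, state in Sections 5.0 and 6.0 that JAR recruitment is limited to children under the SCH service, and say so in the JAR mailing.

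In either case, apply the same screening to both routes. The JAR form should cover every inclusion and exclusion criterion. A clinical co-investigator should review eligibility, including the JIA diagnosis, before consent, and Section 6.0 should state who does this and from what source.

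The cost is an amended criterion or recruitment text, a longer form, and a small amount of clinical time per JAR family. Section 12.0 already assigns the SCH co-investigators to identifying and recruiting patients. If the criterion is widened, there is also some travel, since Section 5.0 plans in-person prototype training and return of the devices to SCH. Separate reporting by recruitment route is not needed to repair this defect, and with 25 children it would leave very small groups.

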3.0 Clinical need

Juvenile Idiopathic Arthritis (JIA) is a paediatric long-term condition affecting approximately 15,000 children and young people (CYP) in the UK, with 1,000-1,5000 new diagnoses each year. It causes ongoing joint inflammation, pain and stiffness, making everyday activities difficult. It affects every aspect of CYP's lives, impacting on physical, social, emotional and education development, with widespread lack of understanding often making CYP with JIA feel isolated. There are products designed to support CYP with JIA but they have limitations and our previous work (a survey and co-design process conducted in 2018) shows they are not sensitive to user needs. Our survey highlighted that CYP with JIA find these products difficult to use as most therapeutic aids are targeted towards an adult population. The few that are aimed at children were seen as patronising and stigmatising. These products also often neglect to take into account the wider stakeholder network such as parents, teachers and healthcare professionals, and therefore neglects to support them in helping CYP with JIA.

Key stakeholder groups (CYP with JIA, their parents, healthcare professionals and teachers) were active participants throughout our previous work, through co-design workshops and surveys. The key highlighted clinical need was assistance with self-management.

This is broken down into the following specific unmet needs:

- Pain-management. Improved pain management would enable CYP to do more of the things they love, by providing a solution that they can use independently as and when is needed, positively impacting their wellbeing.
- Physiotherapy adherence as currently CYP often do not do clinician-recommended exercises. Improved compliance with recommended physiotherapy interventions may reduce pain in the long-term and improve mobility.
- Communication between the pupil and teacher. Improving this communication would provide CYP with a way to discreetly access necessary support without facing stigma, improving their concentration by removing anxiety around accessing help

As a result, 'JIA Toolbox' was co-designed and developed to fulfil these needs and previously tested on a cohort of n=10 CYP with JIA during a proof-of-concept study. The results from

the proof-of-concept study were successful with 80% of participants finding one or more of the prototypes beneficial for their condition management.

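### The computer-and-internet inclusion criterion rests on co-design workshops that are not part of this study and, as written, refuses families who have only a phone or tablet

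*Protocol*

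**What the plan says.** Protocol section 6.1 lists among the inclusion criteria: "Access to a computer with an internet connection to facilitate virtual co-design workshops due to the COVID-19 pandemic". That is the only reason given for it.

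Section 5.0 sets out the participant steps under WP4, WP5 and WP6. One is labelled virtual, "5.2 Virtual training session on data collection processes for participants (1 hour" (bracket closed in the original), and one in person, "5.4 In person training session on prototypes (1- 1.5 hours" (likewise). The text below the list confirms the number: "There will be two training sessions, one on how to use the data collection packs", the other being on the prototypes. The closing contact is "5.8 End of intervention interview (1 hour 1:1 with researcher" (likewise), with no mode stated.

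Section 3.0 describes co-design as already done. The stakeholder groups "were active participants throughout our previous work, through co-design workshops and surveys", and the same section refers to "a survey and co-design process conducted in 2018".

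Section 6.0 shows where eligibility is applied. Clinical members of the team screen families at the hospital, and the JAR form asks about age and the other inclusion criteria. It also shows some reliance on email at the hospital: "A consent form (shown in appendix 9, 10 and 11) will then be emailed to be signed and sent back".

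**The concern.** An eligibility rule should rest on something the participant will be asked to do. Here the stated reason is an activity that the schedule does not contain, during a pandemic that section 14.0 treats as past and that does not fit a study period running from April 2024 to July 2025. The wording looks carried over from another project.

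It is not just a stray phrase, because it sits in the list used for screening at both recruitment sources. Read literally, it asks for a computer, so a family that goes online only by phone or tablet does not qualify.

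That sits badly with the study's purpose. Section 1.0 describes a real-world setting, and section 15.0 counts early discovery of barriers to adoption among the benefits of the design. Section 6.0 even treats a teacher's refusal as useful information on adoption. A restriction on household equipment narrows who is observed. Section 6.1 explains its exclusions for autism, other pain disorders and other joint or muscle disorders, but this restriction has only a reason that no longer applies.

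**Working it through.** No arithmetic decides this point, and the plan gives no figure to reproduce. The check sets the criterion's reason against each step in section 5.0, with section 6.0 for recruitment and consent.

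| Step | Mode stated | Co-design workshop? | Computer named? |
|---|---|---|---|
| 4.1–4.2 Recruitment and consent | Calls and emailed forms (section 6.0) | No | No |
| 5.1 Device testing by clinical engineering | No participant role stated | No | No |
| 5.2 Data collection training, 1 hour | Virtual | No | No |
| 5.3 Baseline data, 2 weeks | Not stated | No | No |
| 5.4 Prototype training, 1 to 1.5 hours | In person | No | No |
| 5.5 Device use, 3 months, with weekly check-ins | Check-in mode not stated | No | No |
| 5.6 Return of devices | To the hospital | No | No |
| 5.7 Post-intervention data, 2 weeks | Not stated | No | No |
| 5.8 Interview, 1 hour, one to one | Not stated | No | No |
| 6.1 Analysis | By the research team | No | No |

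**Count.** There are 0 co-design workshops, 1 step labelled virtual, and 0 steps that name a computer.

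**Earlier work packages.** WP1 to WP3 are not described. Participants are recruited in WP4, so a workshop before that could not justify a criterion for them.

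**Other uses of online access.** There are three: item 5.2, the emailed consent form, and the JAR registration form sent by email. Each supports a need for some way of going online. None is said to require a computer rather than another device.

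**Order of steps.** Item 5.2 comes before the 2-week baseline (5.3), and 5.3 comes before the in-person session (5.4). Section 5.0 compares baseline data with data collected while the devices are in use. Training in data collection given at 5.4 would therefore come after the baseline it is meant to prepare for.

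**Number of families.** If a share p of otherwise eligible families lacks a computer, filling 25 places means turning away about 25 × p/(1 − p) families. The document gives no value for p and nothing from which to derive one, so the count cannot be estimated.

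**The case against.** The strongest reply is that only the reason is out of date and the requirement is still useful. Training at 5.2 is virtual, and recruitment and consent lean on email. The weekly check-ins and the final interview may be remote too, since their mode is not stated, and the data collection packs are in an appendix that is not at hand. On this view an editorial correction is enough.

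Much of that stands, and it rules out several stronger readings that a reader might infer:

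- *Families are excluded solely for something that will not happen.* This is true of the stated reason only. Online access serves steps that will take place.
- *A family with only a phone, or with poor internet, could complete every step.* This cannot be verified while the modes of the check-ins and interview and the content of the packs are unknown. For poor internet it is doubtful, because 5.2 is virtual.
- *The results would overstate ease of adoption.* Section 2.0 describes devices that heat, vibrate or light up, and mentions no app or home internet for using them. A link from computer ownership to uptake, and its direction, is conjecture.
- *A definite number of families is lost.* Any figure would be a guessed share put through a formula. Emailed forms already depend on online access, so the further loss due to this criterion may be small.

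What the reply does not rescue is the word computer. The known uses support, at most, a requirement for some internet-enabled device.

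**Conclusion.** The criterion is wrong as written: its stated basis is absent from the study, and its literal terms are narrower than any listed step is shown to need. The consequence is the avoidable refusal of families who have a phone or tablet but no computer.

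The point is minor. The extent of the refusal and any resulting bias are unknown, and neither the planned 25 participants nor the stop/go percentages in section 9.0 are affected. The conclusion assumes that the steps in section 5.0 are the complete participant schedule and that screening applies section 6.1 literally. It would weaken if an appendix that is not shown made a computer necessary for some step, but the criterion should then give that step as its reason.

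**What to change.** In section 6.1, delete the reference to co-design workshops and COVID-19. Restate the criterion as being able to join the 1-hour data collection training (item 5.2) by any internet-enabled device, or by telephone if the packs can be explained that way. Put the same wording on the JAR registration form.

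Any alternative delivery should be fixed before the 5.3 baseline starts and should not be combined with session 5.4. No in-person contact before baseline is listed, so a face-to-face alternative would need an extra visit.

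If the study team does need a computer for a step, it should name that step in the criterion.

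The cost is one line in the protocol, one line on the JAR form, and perhaps a telephone session for an occasional family.
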